### **2.5.3 Handling of missing values/censoring/discontinuations**

In the primary analysis, no imputation will be used for any patients, who discontinue study therapy due to adverse events or abnormal laboratory values. All patients who prematurely discontinue, and do not achieve and maintain the target dose of LCZ696 200 mg bid at 10 weeks after randomization will be regarded as 10 week up-titration failures. Information of patients discontinuing study drug or participation in trial visits will be collected whenever possible and will be used in the analysis. In patients who could not be followed up for the primary endpoint, it is aimed to at least determine the vital status of the patients at the final visit.

### **2.5.4 Supportive analyses**

In addition to the primary analysis, a supportive analysis will be carried out, based on evaluable patients in the SAF population where patients with administrative discontinuations (non-AE or non-death reasons) will be considered as non-evaluable, and thus excluded.

As a further supportive analysis, the primary analysis, will be repeated using the FAS population instead of the SAF population,

## **2.6 Analysis of the key secondary objective**

There is no key secondary objective.

## **2.7 Analysis of secondary efficacy objective(s)**

There are no other secondary efficacy objectives to be analyzed.

## 2.8 Safety analyses

The following secondary variables will be used in the analyses:

- Achieving and maintaining either the dose of 100 mg and/or 200 mg LCZ696 bid for at least 2 weeks leading to week 10 after randomization, regardless of previous dose interruption or down-titration during the 10-week after Randomization (Yes/no)
- Achieving and maintaining any dose of LCZ696 for at least 2 weeks leading to week 10 after randomization, regardless of previous dose interruption or down-titration during the 10-week after Randomization (Yes/no)
- Permanently discontinuation from study drug (Yes/no) at any time between Randomization and week-10 after randomization due to Adverse Events

These secondary variables will be analyzed in an identical fashion to the primary variable (using the stratified Cochran-Mantel-Haenszel method; see 2.5.2 for details).

### 2.8.1 Adverse events (AEs)

The incidence of treatment emergent adverse events (events occurred between the first dose and the last dose of study medication, including those occurred on the first dose date or last dose date of study medication) will be summarized by primary system organ class and preferred term. Additional summaries will be provided by severity and relationship to study medication. As the analysis of treatment emergent AEs will most likely lead to a higher frequency in the pre-discharge group, due to the longer exposure duration as well as the early exposure in a well-monitored hospital setting, an additional analysis of AEs since randomization will be carried out in the FAS population; for this analysis, AEs are defined as events occurred between the randomization date and the last dose of study medication that were absent pre-randomization, or events present prior to randomization but increased in severity after randomization.

Adverse events occurring after the last dose of study medication will be summarized by primary system organ class and preferred term.

Adverse events will be reported by primary system organ class and preferred term and separately by SMQ according to the Medical Dictionary for Regulatory Activities (MedDRA).

The MedDRA version used for reporting the study will be described in a footnote.

If a subject reported more than one adverse event with the same preferred term, the adverse event with the greatest severity will be presented. If a subject reported more than one adverse event within the same primary system organ class, the subject will be counted only once with the greatest severity at the system organ class level, where applicable.

The number and percentage of subjects reporting any adverse event and adverse events adjusted for exposure during the double-blind period of the study will be summarized by primary system organ class, preferred term and treatment and also by SMQ and treatment. The most common adverse events reported ( 1 % in any group for each preferred term in the SOC-PT table or 1% in any group for each SMQ table) will be presented in descending frequency according to its incidence in <treatment group xxx > starting from the most common event.

Separate summaries will be provided for study medication related adverse events, death, serious adverse event, other significant adverse events leading to discontinuation and adverse events leading to dose adjustment.

Three periods will be considered for the AEs analysis:

- 10 weeks of treatment epoch which is defined as the initial 10 weeks after randomization: all AEs started during the 10 weeks of treatment epoch will be included;
- 16-weeks follow-up epoch which is defined as the additional 16 weeks after the treatment epoch: all AEs started during the follow-up epoch will be included;
- 26 weeks duration which is defined as the whole study from the randomization date up to the end of study date.

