The study consists of three Epochs (phases): the *Screening Epoch*, the *Treatment Epoch*, and the *Follow-up Epoch*. The *Screening Epoch* is defined as the time from administration of ICF and up to the time of *Randomization*, which is expected to range between 1 and 3 days. When admitted for acute decompensated HF, conventional therapy is started or continued at the discretion of the treating physician and is performed until hemodynamic stability is achieved. *Randomization* will occur only after the 24h stabilization interval is completed. The *Treatment Epoch* is identified as the initial 10 weeks after Randomization. The *Follow-up Epoch* is identified as the continuation of open-label LCZ696 treatment for additional 16 weeks after the *Treatment Epoch* to further evaluate safety and tolerability.

In this study, last contact with the subject will be the end of study visit, unless an SAE occurs (see below). However, to ensure patient safety, every SAE must be reported to Novartis:

- occurring until 30 days after the last study visit, regardless of causality
- occurring after the 30 days period, if a causal relationship to study treatment is suspected

The on-treatment period exposure is defined as:

- Date of last study drug intake – first study drug intake + 1

In general, treatment emergent AEs are defined as events starting after the first dose of study treatment that were absent pre-treatment, or events present prior to the first dose but increased in severity after the first dose. This assumes the same AE with increased severity is properly entered as a separate record in the database with start date being the date when severity increases and that a second AE with same severity won't be entered before the same AE is resolved.

For any other safety analyses based on abnormalities post-baseline compared to baseline (i.e. ECGs, vital signs, etc.), where either of the results is not available, the *missing* category will be included to avoid any abnormalities being overlooked.

The following regions will be defined:

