##### 5.1.2.2 Adverse Event Start Date Imputation

###### Rules for imputing the AE start date

The following table explains the notation used in the logic matrix. Please note that **missing start dates** will not be imputed.

	Day	Month	Year
Partial Adverse Event Start Date	Not used	MON	YYYY
Treatment Start Date	Not used	TRTM	TRTY

The following matrix explains the logic behind the imputation.

	MON MISSING	MON < TRTM	MON = TRTM	MON > TRTM
YYYY MISSING	( 1 ) No convention	( 1 ) No convention	( 1 ) No convention	( 1 ) No convention
YYYY < TRTY	( 2.a ) Before Treatment Start	( 2.b ) Before Treatment Start	( 2.b ) Before Treatment Start	( 2.b ) Before Treatment Start
YYYY = TRTY	( 4.a ) Uncertain	( 4.b ) Before Treatment Start	( 4.c ) Uncertain	( 4.c ) After Treatment Start
YYYY > TRTY	( 3.a ) After Treatment Start	( 3.b ) After Treatment Start	( 3.b ) After Treatment Start	( 3.b ) After Treatment Start

Before imputing AE start date, find the AE start reference date.

1. If the (imputed) AE end date is complete and the (imputed) AE end date < treatment start date then AE start reference date = min (informed consent date, earliest visit date).
2. Else AE start reference date = treatment start date

Impute AE start date -

1. If the AE start date year value is missing, the date uncertainty is too high to impute a rational date. Therefore, if the AE year value is missing, the imputed AE start date is set to NULL.
2. If the AE start date year value is less than the treatment start date year value, the AE started before treatment. Therefore:
  - a. If AE month is missing, the imputed AE start date is set to the mid-year point (01JulYYYY).
  - b. Else if AE month is not missing, the imputed AE start date is set to the mid-month point (15MONYYYY).
3. If the AE start date year value is greater than the treatment start date year value, the AE started after treatment. Therefore:
  - a. If the AE month is missing, the imputed AE start date is set to the year start point (01JanYYYY).
  - b. Else if the AE month is not missing, the imputed AE start date is set to the later of (month start point (01MONYYYY), AE start reference date + 1 day).
4. If the AE start date year value is equal to the treatment start date year value:
  - a. And the AE month is missing the imputed AE start date is set to the AE reference start date + 1 day.
  - b. Else if the AE month is less than the treatment start month, the imputed AE start date is set to the mid-month point (15MONYYYY).

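### The SAP's since-randomization AE analysis ends at the last dose rather than at a fixed time, and its partial-date rules never refer to randomization

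*SAP*

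**What the plan says.** SAP 2.8.1 expects the treatment-emergent analysis to show more AEs in the Pre-discharge arm, "due to the longer exposure duration as well as the early exposure in a well-monitored hospital setting". It therefore adds an analysis since randomization in the FAS, in which "AEs are defined as events occurred between the randomization date and the last dose of study medication that were absent pre-randomization" (or worsened after randomization). The next paragraph adds: "Adverse events occurring after the last dose of study medication will be summarized by primary system organ class and preferred term".

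The same section then lists three reporting periods. For the 10-week epoch, "all AEs started during the 10 weeks of treatment epoch will be included". The last is the "26 weeks duration which is defined as the whole study from the randomization date up to the end of study date". Neither mentions the last dose. SAP 2.1.1 describes treatment-emergent AEs in general as "events starting after the first dose of study treatment that were absent pre-treatment" (or worsened after it), with no end date, whereas SAP 2.8.1 closes that window at the last dose.

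For AE start dates with a missing day, SAP 5.1.2.2 uses the consent or earliest visit date as reference if the AE ended before first dose. Otherwise, "Else AE start reference date = treatment start date". Within the treatment-start year, rule 4.b reads: "Else if the AE month is less than the treatment start month, the imputed AE start date is set to the mid-month point". For the same or a later month, rule 4.c takes the later of the first of the month and the reference date plus one day.

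Protocol section 6 keeps patients who permanently stop drug in the Treatment Epoch on all remaining visits up to Visit 199, with no Follow-up Epoch. Protocol 5.5.9 treats stopping during the Follow-up Epoch as withdrawal.

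**The concern.** The analysis was added so that the arms could be compared over similar time. It corrects the start of the window but not its end. Last dose is a post-randomization outcome, and stopping because of AEs is itself a secondary endpoint (SAP 2.8). The length of observation is therefore tied to the tolerability being compared: the arm that stops more contributes less time and so fewer counted events.

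The reporting periods do not settle the matter. One reader could count every AE in the 10 weeks; another could apply the last-dose limit within the 10 weeks. The two tables would differ.

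A second misalignment lies in the partial-date rules. An analysis anchored on randomization uses dates imputed around treatment start, and treatment start is exactly what differs between the arms.

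**Working it through.** The plan gives no figure on this point, so there is none to reproduce.

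**Window length.** Inputs:
- Horizon: T = 70 days, the Treatment Epoch.
- Pre-discharge first dose: no later than 7 days after randomization (Protocol 3.1).
- Post-discharge first dose: 1 to 14 days after discharge, or 12 to 21 days after randomization if the stay is prolonged (Protocol 3.1).
- Stopping rate: none is given for this trial. Protocol 3.6 reports 10.4% permanent discontinuation over a median of 29 days in the run-in of the earlier LCZ696 versus enalapril trial. I use it for illustration, with half and double as the range.

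Assume a constant stopping hazard h from first-dose day s. The mean time from randomization to last dose, cut at T, is

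W = s + (1 − exp(−h(T − s)))/h, with h = −ln(1 − 0.104)/29 = 0.00379 per day.

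- Pre, s = 2: 2 + (1 − exp(−68h))/h = 62.0 days, so 8.0/70 = 11.5% is not counted.
- Post, s = 10: 10 + (1 − exp(−60h))/h = 63.7 days, so 6.3/70 = 9.0% is not counted.
- With h = 0, W = 70 days in both arms. The treatment-emergent window would then be 68 versus 60 days, so the added analysis does remove the start-date imbalance.

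Post minus Pre window, in days, with the same hazard in both arms:

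| First-dose day, Pre/Post | Half hazard | 10.4% per 29 days | Double hazard |
|---|---|---|---|
| 0/3 | 0.4 | 0.7 | 1.2 |
| 2/10 | 0.9 | 1.7 | 3.1 |
| 2/16 | 1.5 | 2.9 | 5.2 |
| 7/21 | 1.4 | 2.7 | 4.8 |

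Unequal stopping by week 10 (assumed), with starts on Day 2 and Day 10 and h = −ln(1 − p)/(70 − s):

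| Stopping, Pre/Post | Mean window, days | Not counted |
|---|---|---|
| 10%/10% | 66.5 / 66.9 | 4.9% / 4.4% |
| 15%/10% | 64.8 / 66.9 | 7.5% / 4.4% |
| 20%/10% | 62.9 / 66.9 | 10.1% / 4.4% |

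**Partial dates, example with assumed dates.** Both patients have an AE recorded only as September.
- A Post-discharge patient is randomized on 20 September and first dosed on 4 October. The AE month precedes the treatment month, so rule 4.b gives 15 September. That is before randomization, so the AE is not counted.
- A Pre-discharge patient is first dosed on 22 September. Rule 4.c gives 23 September, and the AE is counted, provided it did not end before first dose.

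**Partial dates, size.** I simulated the rules for AEs with only the start day missing and a known end date. Assumptions: consent 1 to 3 days before randomization; discharge 2 to 7 days after it; Pre first dose before discharge; Post first dose 1 to 14 days after discharge; AE starts uniform over 70 days; mean AE duration 5 or 14 days.
- Post-randomization AEs imputed to before randomization: 5.8% to 7.6% in the Post arm, 0.4% to 0.6% in the Pre arm.
- AEs that truly began before randomization but are imputed into the window: 56% to 75% in the Pre arm, 21% to 35% in the Post arm.

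These are percentages of partly dated AEs only. The documents do not give their number.

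**The case against.** The strongest reply is that the plan already reports what this analysis omits. AEs after the last dose have their own summary, deaths are flagged as on-treatment or post-treatment (SAP 2.8.2), and the 10-week period read literally is close to the fixed-window table one would want. Safety is descriptive, with no formal inference (Protocol 9.5.2).

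Most of this stands, and it rules out several stronger readings that a reader might infer:
- *Post-stopping AEs are lost.* They are not; they are only outside this comparison. The separate table does not fully replace it. No population or end date is stated for it, and a patient with the same event before and after stopping would appear in both tables, so patient-level incidence cannot be obtained by adding them.
- *This is the plan's only fair safety comparison.* The 10-week period and the AE-discontinuation endpoint from randomization to week 10 both prevent that claim.
- *The windows differ between arms by design.* They are equal for patients on drug at Day 70.
- *Never-dosed patients sit in the FAS with no window.* SAP 2.2 and Tables 5-1 and 5-2 exclude from the FAS anyone not starting within the protocol windows (OTH13), which on its plain wording covers them. Table 5-1 does list never-dosed patients separately (TRT04) as an SAF exclusion only, so the overlap needs stating.
- *Anchoring on treatment start removes events.* Dating an AE to the day after treatment start normally keeps it inside the window. The loss comes from the mid-month and consent-date branches.

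It is also fair to say that the SAP 2.1.1 wording is general and concerns treatment-emergent AEs, not the since-randomization analysis. What does not fall away is the explicit last-dose limit and the silence on how it combines with the reporting periods.

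**Conclusion.** The point holds as a defect of definition in one descriptive analysis. The last-dose limit makes the window depend on stopping drug and leaves out AEs that the protocol collects to Visit 199. With equal stopping hazards the arm difference is 0.4 to 5.2 days of 70 over the assumed range, and 1.7 days in the central case. It reaches 4.0 days (66.9 − 62.9) if 20% versus 10% stop by week 10. These figures rest on assumed first-dose days, a constant hazard and a borrowed stopping rate. They show that the distortion grows when tolerability differs, which is when the table matters most. They do not show that it would reverse a conclusion.

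The partial-date error is real and runs mainly against counting Post-discharge events. Its overall weight is unknown, because the number of partly dated AEs is not given.

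**What to change.** In SAP 2.8.1, for the since-randomization analysis in the FAS, count AEs from randomization to Day 70 (Visit 199) regardless of last dose. The last-dose version can be kept as an on-treatment supplement.

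In SAP 5.1.2.2, add that partial AE start dates for this analysis are imputed relative to the randomization date.

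Reconcile the AE windows in SAP 2.1.1 and 2.8.1: give one end date for treatment-emergent AEs, and say which cut-off governs within the 10-week, 16-week and 26-week periods. In SAP 5.5, state whether TRT04 patients fall under OTH13 for the FAS.

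Do not carry the fixed window to week 26. Patients who stop in the Treatment Epoch have no visits after Visit 199, and those who stop later are withdrawn (Protocol 5.5.9 and section 6), so largely unobserved time would be read as event-free.

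The cost is SAP wording and some reprogramming of dates and tables. No new data are needed, because AEs after stopping in the Treatment Epoch are already collected to Visit 199.

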### 2.8.1.1 Adverse events of special interest / grouping of AEs

The characteristics of the following adverse events of special interest will be summarized as appropriate, using relative frequencies.

**Table 2-3 Adverse events of special interest**

AE of special interest	Definition: MedDRA preferred term / eCRF form
Hypotension events	Hypotension Orthostatic hypotension Presyncope Dizziness Dizziness postural Syncope Blood pressure decreased Syncope vasovagal Vertigo Vertigo positional
Hyperkalemia events	Hyperkalaemia Serum potassium increased Blood potassium increased
Renal dysfunction events	All events captured in the renal questionnaire event pages of the CRF

Only the adjudicated angioedema (as adjudicated by the adjudication Committee) reported during treatment and follow-up periods will be presented.

The information is derived from the first page of the Angioedema questionnaire, after the Adjudication committee has completed and the adjudication is = Yes.

For all events, please refer to the table for specific angioedema questionnaires details.

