3.6 Risks and benefits

Risks associated with participation in this study are primarily associated with potential side effects of the study drug LCZ696, which are comparable to other proven HF treatments, such as ACEI, ARBs, and MRA, including events like hypotension, renal impairment, hyperkalemia, angioedema.

To date, over 15,000 subjects have taken LCZ696 in studies that have been performed in healthy subjects and patients with hypertension, heart failure with preserve ejection fraction, and heart failure with reduced ejection fraction.

In PARADIGM-HF study the overall incidence of adverse drug reactions to LCZ696 in heart failure patients was comparable to that seen with enalapril. During PARADIGM-HF LCZ696 up-titration run-in phase (median drug exposure 29 days), 10.4% of patients permanently discontinued, 5.9% because of an adverse event, most commonly renal dysfunction (1.8%), hypotension (1.7%) and hyperkalemia (1.3%). However, discontinuation of therapy due to an adverse event in the double-blind period of the PARADIGM-HF study occurred in 10.7% LCZ696-treated patients and in 12.2% enalapril-treated patients. The events most commonly associated with dosage adjustment or treatment interruption were hypotension, hyperkalemia and renal impairment.

Risk of hypotension

Cases of symptomatic hypotension have been reported in patients treated with LCZ696 during clinical trials, especially in patients \geq 65 years old, patients with renal disease and patients with low SBP (< 112 mmHg). Patients with SBP < 100 mmHg were not studied, therefore LCZ696 therapy should not be initiated until SBP is \geq 110 mmHg.

A higher rate of symptomatic hypotension was observed with LCZ696 than with enalapril in the CLCZ696B2314/PARADIGM-HF trial. However, there was no increase in the rate of discontinuation because of possible hypotension-related adverse effects. Other hypotension-related SAEs, including syncope, dizziness, loss of consciousness, and orthostatic hypotension, were infrequent and occurred at a comparable incidence with enalapril. Hypotension was reversible and manageable with dose adjustment or temporary treatment interruption.

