Data from vital signs including body weight will be summarized as appropriate, , using both descriptive summary statistics, and various threshold flags; incidences of notable values will be presented in the tables and notable values will be flagged in the listings.

The following ECG variables will be summarized as appropriate, using both descriptive summary statistics and qualitative changes will be described.

Safety analyses will be performed based on the safety population. There will be no formal statistical inference analysis.

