### 2.8.4.2 Vital signs

Data from vital signs will be summarized by reporting descriptive summary statistics for both actual and change from baseline at each available visit with visit 101 as baseline; furthermore, various threshold flags will also be used to determine incidences of notable values, which will be presented in tables and notable values will be flagged in the listings.

Patients with notable vital signs as defined below will be summarized:

- Pulse rate:
  - Low:  $\leq 50$  bpm and decrease from baseline higher or equal to 15 bpm
  - High:  $\geq 120$  bpm and increase from baseline higher or equal to 15 bpm
- Systolic blood pressure (SBP):
  - Low:  $\leq 90$  mmHg and a decrease from baseline higher or equal to 20 mmHg
  - High:  $\geq 180$  mmHg and increase from baseline higher or equal to 20 mmHg
- Diastolic blood pressure:
  - Low:  $\leq 50$  mmHg and a decrease from baseline higher or equal to 15 mmHg
  - High:  $\geq 105$  mmHg and increase from baseline higher or equal to 15 mmHg.

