## 2.11 Interim analysis

Two interim analyses of tolerability and safety will be carried out during the study when 30% and 60% of the patients have completed the visit at 10-weeks after Randomization (Visit 199).

Details will be pre-specified in the Charter of the DMC.

The review will include the following analyses:

- AEs leading to permanent discontinuation of LCZ696
- AEs reported leading to down-titration of LCZ696 or temporary discontinuation
- Incidence of AEs of interest
- Concomitant medication changes when down-titration was implemented
- Compliance with the washout from ACEi or discontinuation of ARBs

The DMC will also monitor all adverse outcomes during the trial and weigh them against the potential benefits of treatment. The DMC will in particular monitor:

- Angioedema
- Hyperkalemia
- Liver and Renal Dysfunction
- Hypotension
- Pregnancy

When considering whether to stop any active treatment arm of LCZ696 for safety concerns the following points should be considered

- whether observed adverse trends are compelling in terms of the amount of evidence
- whether observed adverse trends outweigh the potential benefits of treatment.

If the study is terminated, all ongoing patients will be brought in for the end of study visits. Those incomplete patients which do not get to Week 10 (Visit 199) as a result of DMC study termination by the DMC, will be excluded from both the primary analysis and the supplementary primary analysis.

To ensure the DMC is provided all required information and to ensure the proper execution of the interim analysis an interim analysis plan will be prepared. This analysis plan will include a description of all statistical analyses to be conducted, specifications for the analysis data sets and the layout of tables, figures and listings. Analyses will be planned and conducted as specified in the Clinical Trial Protocol, unless specific monitoring requirements of the DMC necessitate a different approach. The Novartis trial team will be given the opportunity to provide comments and recommendations and the Novartis list of mandatory tables for a DMC safety report will be included.

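### The SAP's hypotension event of special interest leaves out loss of consciousness, which the protocol itself names as hypotension-related, so that grouped count can be slightly too low

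*SAP*

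**What the plan says.** SAP section 2.8.1.1 introduces Table 2-3 with: "The characteristics of the following adverse events of special interest will be summarized as appropriate, using relative frequencies". In that table the hypotension row is defined by preferred terms: "Hypotension Orthostatic hypotension Presyncope Dizziness Dizziness postural Syncope Blood pressure decreased Syncope vasovagal Vertigo Vertigo positional". Nothing in the row marks the ten terms as examples, so the list is closed.

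Protocol section 3.6, under the risk of hypotension, describes experience in the earlier heart failure trial: "Other hypotension-related SAEs, including syncope, dizziness, loss of consciousness, and orthostatic hypotension, were infrequent". Protocol section 6.5.3 names hypotension as an adverse event of interest for this study but gives no list of terms.

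SAP section 2.11 puts "Incidence of AEs of interest" among the analyses for the two interim reviews and names hypotension as a topic that the DMC will monitor. SAP section 4, on changes to the protocol's analyses, does not mention the hypotension grouping.

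**The concern.** The protocol and the SAP describe the same safety topic with different sets of events. The protocol treats loss of consciousness as a hypotension-related event, on the same footing as syncope. The SAP, which fixes what is counted, leaves it out and does not say why.

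At stake is one grouped count on a named safety topic. Readers of the report will take the hypotension line as the number of patients with any hypotension-type event. It cannot be repaired exactly from the other tables: one patient can have several terms, so preferred-term rows cannot simply be added to it. The interim reviews also look at events of interest, and Protocol section 9.6.1 sets no stringent stopping boundaries, so displayed counts inform judgement directly.

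**Working it through.** The plan states no figure on this point, so there is none to reproduce. The main check compares the terms.

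| Event named in Protocol 3.6 | In the hypotension row of SAP Table 2-3? |
|---|---|
| Orthostatic hypotension | yes |
| Dizziness | yes (also the postural form) |
| Syncope | yes (also the vasovagal form) |
| Loss of consciousness | **no** |

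Three of the four named events are listed and one is not. This is a count of event types. It does not mean that a quarter of the patients are missed.

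**How many patients could be left out.** The documents give no rate of loss of consciousness, so the following inputs are assumptions, except the arm size. Arm size is about 500, from about 1000 patients randomised 1:1 (SAP sections 1.1 and 3). Let *l* be the post-discharge rate of loss of consciousness, taken as 0.1 to 1%, and *r* the pre-to-post ratio of that rate, taken as 1 to 2. If no such patient has another listed term:

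left out = 500 × *l* × (1 + *r*)

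- Low end: 500 × 0.001 × (1 + 1) = 1 patient.
- High end: 500 × 0.01 × (1 + 2) = 15 patients.

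Both are upper bounds for their inputs, because a patient who also has, say, syncope or hypotension coded is already counted.

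**How far the arm contrast could move.** Suppose the ten-term group occurs in 10% of post-discharge and 12.5% of pre-discharge patients (ratio 1.25). Adding loss of consciousness gives (0.125 + *l* × *r*) / (0.10 + *l*).

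- *l* = 1%, *r* = 1: 0.135 / 0.110 = 1.23. The difference stays at 2.5 percentage points.
- *l* = 1%, *r* = 2: 0.145 / 0.110 = 1.32. The difference rises from 2.5 to 3.5 points.
- *l* = 0.1%, *r* = 1 to 2: 0.126 / 0.101 = 1.25 to 0.127 / 0.101 = 1.26.

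**The two vertigo terms.** Table 2-3 also lists vertigo and positional vertigo, which the sentence in Protocol 3.6 does not name. If they added *v* equally to both arms, with no overlap with other listed terms, the ratio would shrink. From 15% against 10%, *v* = 1% gives 16/11 = 1.45 and *v* = 3% gives 18/13 = 1.38, against 15/10 = 1.50. The difference is 5 points in every case. All these rates are assumed, and so are the equality between arms and the absence of overlap.

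**The case against.** The strongest reply is that the SAP contradicts no protocol definition. The sentence in Protocol 3.6 is background on an earlier trial, its list is open, and the protocol leaves the choice of terms to the SAP. That is correct, so this is not a breach of the protocol. It does not remove the mismatch, because loss of consciousness is named positively as hypotension-related and the SAP gives no reason for dropping it.

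The second reply is that the events are reported anyway. A reader might infer from the omission that serious events go unseen, and the documents do not support that. The SAP states: "Adverse events will be reported by primary system organ class and preferred term and separately by SMQ". It also states: "Separate summaries will be provided for study medication related adverse events, death, serious adverse event". For measured blood pressure, section 2.8.4.2 states: "Patients with notable vital signs as defined below will be summarized". What is affected is the grouped hypotension count. The protocol also calls these serious events infrequent.

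A reader might also infer that the vertigo terms dilute the comparison between arms. The documents do not establish this. Absence from an open list does not show that vertigo is unrelated to hypotension; presyncope and decreased blood pressure are not named in that sentence either. No rates are given, events of special interest are shown as relative frequencies, and of the safety analyses the protocol says: "There will be no formal statistical inference analysis". A narrower grouping would also need care: one without dizziness would drop an event that Protocol 3.6 names.

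Finally, titration rests on the investigator's judgement (Protocol section 5.5.4), not on this grouping. The DMC also reviews events leading to discontinuation or down-titration and monitors all adverse outcomes. Its charter and the interim analysis plan are separate documents, so how far Table 2-3 shapes its reports is not known.

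**Conclusion.** The point holds in a limited form. Table 2-3 omits one of the four events that Protocol 3.6 calls hypotension-related, without explanation, and a patient with only that event is missing from the hypotension summary. The mismatch can be read directly from the text and rests on no assumption. Its size does: about 1 to 15 patients per 1000 under the assumed rates, as an upper bound, with a group ratio of 1.25 moving to somewhere between 1.23 and 1.32. No primary or secondary endpoint and no planned test is affected. The change is still worth making, because hypotension is a named safety topic that the DMC follows and the correction costs almost nothing.

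Two stronger conclusions are not supported: that serious events disappear from the report, and that the vertigo terms bias the arm comparison towards no difference. Whether vertigo belongs in the group is a coding judgement that the documents leave open.

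**What to change.** Add *Loss of consciousness* to the hypotension row of SAP Table 2-3, checking the exact preferred term in the MedDRA version in use. Use the same list for the events of interest in the DMC reports. If the omission was deliberate, give the reason beside the table instead.

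Optionally, show the count without the two vertigo terms as a sensitivity display. Keeping the present ten-term count beside the revised one would make the effect of the change visible.

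The cost is one line of SAP text and a re-run of the tables for events of special interest. SAP Amendment 4 already revised the hyperkalemia and renal dysfunction definitions before the final database lock, so a change of this kind has a precedent. The downside is a slightly higher and possibly less specific count, since loss of consciousness can have causes other than low blood pressure.
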